In the beginning of 2021, large-scale severe acute respiratory syndrome coronavirus 2 (SARS-CoV-2) vaccination campaigns were initiated in European countries, resulting in a high coverage of primary vaccination, e.g., 83% and 92% of respectively the population of Belgium and Aragon (Spain) older than 5 years (i.e., eligible to be vaccinated) had received at least a complete primary vaccination schedule by the end of 2022 (1,2).

To assess the effectiveness of primary vaccination in preventing different outcomes (i.e., evaluating an intervention effect), randomised controlled trials (RCTs) are considered the "gold standard". However, often we need to resort to observational analyses of existing real-world data when the randomised trial that would answer our causal question - the "Target Trial" - is not feasible, ethical and timely (3). In addition, RCTs have notable limitations of sample size and subgroup analysis, restrictive inclusion criteria, and a highly controlled setting that may not be replicated in a mass vaccine rollout (4). Indeed, RCTs may not reflect the real-world effectiveness (RWE) of the vaccines (5).

Funded by the European Union

Previous real-world observational studies in Europe suggest that the completion of a primary vaccination schedule protects against (symptomatic) infection (4,6-8). The International Vaccine Access Center (IVAC; Johns Hopkins Bloomberg School of Public Health, US) maintains the online VIEW-hub resource (9) which contains real-world epidemiological data on vaccine type and usage, country coverage, and vaccine impact. A living systematic review and meta-analysis is carried out (weekly updated) on the "Post-Authorisation COVID-19 Primary Series Vaccine Effectiveness". However, the real-world studies included in this review encompass a wide range of methodologies, populations, and outcome measures. Indeed, these single-country observational studies are often conducted within (sub)populations with specific characteristics, taking into account different confounding factors and using different statistical methodologies. As such, generalisability and comparability of these results across federations is limited.

Although there is no perfect method for estimating a causal effect in observational data (10), conceptual frameworks exist to guide the design and analysis of observational studies in order to limit apparent paradoxes and common biases and increase the transportability of estimates (3,11). In fact, causal inference from observational databases can be viewed as an attempt to emulate a randomised experiment (the "Target Trial") to answer the question of interest (3). In this study, the effectiveness of SARS-CoV-2 primary vaccination in preventing SARS-CoV-2 infection is assessed across national borders, using a framework for causal inference. The well-defined causal analysis methodology will subsequently be deployed across federations to reproduce the analysis and pool the aggregated results. We aim to inform high-level vaccine policy by leveraging real-world observational data from multiple data sources hosted in multiple sites (i.e., countries).

Research guestion/objectives

We aim to investigate the real-world effectiveness of SARS-CoV-2 primary vaccination as compared to partial or no vaccination in preventing SARS-CoV-2 infection in virtually all resident populations spanning different countries. The study will be conducted in two sequential stages, expanding the exercise to several countries/regions:

- Stage I (pilot): Aragon (Spain) and Belgium.
- Stage II: Aragon (Spain), Belgium, Austria, Finland, Norway, Estonia and The Netherlands. The participation of these countries/regions is conditional on data access.

Methodology

Study design and context

The study design is an observational retrospective longitudinal (cohort) study using routinely collected administrative, social, health and care data from several

countries/regions in Europe. We have designed the observational study to emulate a hypothetical Target Trial (TT) of the causal effect of SARS-CoV-2 vaccination programmes in preventing SARS-CoV-2 infections.

Target Trial specification and emulation

The key components of the target trial and its subsequent emulation are explicitly described in Table 1. Several of the key components are part of the widespread population, intervention, control, and outcome (PICO) approach to the formulation of clinical questions (12).

Protocol Component	Target Trial Specification (Ideal Hypothetical Trial)	Target Trial Emulation (Actual Study Design reusing Real World Data)
Eligibility criteria	 Study population: All individuals eligible to be vaccinated. Enrollment period: From the start of the SARS-CoV-2 vaccination campaign (January 1, 2021) to the start of the SARS-CoV-2 booster vaccination campaign (September 1, 2021). Age: 5 to 115 years old, included (all individuals eligible to be vaccinated). Previous infection: Individuals without a SARS-CoV-2 infection before enrolment. Country: Individuals living in the respective country 	 Study population: All individuals vaccinated with at least one dose of the SARS-CoV-2 vaccine (any of the available brands) and all individuals eligible to be vaccinated with a documented positive diagnosis (irrespective of the type of test) for SARS-CoV-2 infection during the data extraction period. Enrollment period: From the start of the SARS-CoV-2 vaccination campaign (January 1, 2021) until the start of the SARS-CoV-2 booster vaccination campaign (September 1, 2021). Age: 5 to 115 years old, included (all individuals eligible to be vaccinated). Previous infection: Individuals without a documented confirmed infection before completing the primary vaccination schedule (i.e. enrolment) or before January 1, 2021 (SARS-CoV-2 vaccine roll-out) for those not having completed a primary vaccination schedule (controls). Country: Resident of the registered individuals in the COVID-19 cases and vaccination datasets. Individuals with neither a registered vaccine dose nor a positive diagnosis during the data extraction period are therefore excluded.
Treatment strategies	 Primary analysis Completing a primary vaccination schedule (from any vaccine brand) Not completing a primary vaccination schedule (either not receiving a vaccine or being only partially vaccinated). Secondary analysis Completing a homogeneous primary vaccination schedule with 	Same as in Target Trial Specification. Vaccination status ascertainment (including brand, dose and date) based on the vaccination registry. Date of being primary vaccinated (completing a primary vaccination schedule) is considered as 14 days after receiving the final dose of the primary vaccination schedule (one dose for the Johnson-Johnson vaccine and two doses of any of the other vaccines considered).

Table 1. Protocol of the target randomised control trial and target trial emulation by using observational data.

Funded by

BY-COVID is funded by the European Union's Horizon Europe research the European Union and innovation programme under grant agreement number 101046203.

4

Funded by the European Union

	a specific brand (BioNTech-Pfizer, Moderna, Johnson-Johnson, Astrazeneca, Novavax) 2) Not completing a primary vaccination schedule (either not receiving a vaccine or being only partially vaccinated). Pragmatic trial: strategies compared under the usual conditions.	
Assignment procedures	Participants will be randomly assigned, at baseline, to either completing the primary vaccination schedule or to not completing the primary vaccination schedule (no or only partial vaccination). The participants will be aware of the strategy to which they have been assigned (i.e., without blind assignment).	To mimic randomization, we need to adjust for all confounding factors required to ensure comparability (conditional exchangeability) of the groups defined by vaccination (as identified in the Directed Acyclic Graph (13)). We assume that individuals are randomly assigned within levels of baseline covariates: Age, Gender, Comorbidities, ImmuneStatus, EssentialWorker, Foreign, Institutionalised people, Pregnancy, and ResidenceArea. The adjustment will be performed via matching.
Follow-up period	 Starts, for each individual, at randomization to one of the vaccination strategies (baseline) Ends at diagnosis of SARS-CoV-2 infection (i.e., outcome of interest), death, loss to follow-up, the date of receiving a booster dose, 168 days after baseline (24 weeks), or the end of the study period (March 1, 2022), whichever occurs first. 	 Sequential trial emulation: Starts, for each individual: Vaccine group: time of completing a primary vaccination schedule No (or partial) vaccine group: first eligible time (time of completing a primary vaccination schedule of the matched pair) Ends at diagnosis of SARS-CoV-2 infection, death (all causes), vaccination (for unvaccinated controls), completed primary vaccination of the matched control (for vaccinated persons), booster dose (for vaccinated persons), booster dose of the matched vaccinated persons), booster dose of the matched vaccinated person (for unvaccinated controls), or the end of the study period (i.e., the most recent date at which data is available at time of analysis). Loss to follow-up due to emigration or 'disenrollment' from the health care system not taken into account. Newly vaccinated individuals (completing a primary vaccination schedule) are eligible for inclusion in the "vaccine group" of the study, even if they had previously been selected in the "no vaccine group" (as controls).
Outcome	Laboratory-confirmed SARS-CoV-2 infection	A documented laboratory-confirmed SARS-CoV-2 infection, thus excluding self-reported test results
Causal contrast of interest	Per-protocol effect.	Observational analog of the per-protocol effect.

In the target trial (Figure 1), eligible participants are enrolled from January 1, 2021 (start of the SARS-CoV-2 vaccination campaign) until September 1, 2021 (start of the SARS-CoV-2 booster vaccination campaign). As such, the enrolment period in the target trial covers a

Funded by the European Union period of 9 months. For each eligible participant, follow-up starts at the moment of randomisation (baseline, t_0) and ends at diagnosis of SARS-CoV-2 infection (outcome of interest), death, loss to follow-up, receiving a booster dose, or 6 months after baseline. The period of data collection runs until March 1, 2022 to allow for a minimal follow-up period of 6 months for those participants with baseline (t_0) at the end of the enrollment period.

In the sequential emulated target trial (Figure 2), each eligible individual is considered as a different individual at each eligible time (i.e., *daily*). As such, a sequence of nested (*daily*) trials are emulated with increasing time $(t_1, t_2, ..., t_n)$, iterating over the days in the enrollment period. At each eligible time during the enrollment period, the vaccination status of eligible individuals is assessed and every individual who has completed a primary vaccination schedule at that time (treated/exposed) is matched to an individual who has not (yet) completed the primary vaccination schedule (control). Newly vaccinated individuals (completing a primary vaccination schedule) are eligible for inclusion in the study, even if they had previously been selected in the "no (or partial) vaccine group". Follow-up ends at diagnosis of SARS-CoV-2 infection, death, death of matched person, completed primary vaccination (for unvaccinated or partially vaccinated controls), completed primary vaccination of the matched control (for primary vaccinated persons), booster dose (for primary vaccinated persons), booster dose of the matched vaccinated person (for unvaccinated or partially vaccinated controls), or the end of the study period. The study period ends at the most recent date at which data is available at the time of analysis. The data extraction period starts from the date of the first documented SARS-CoV-2 infection, in order to appropriately identify individuals with a previously documented SARS-CoV-2 infection.

[figure not shown]

Figure 1. Timeline of the target trial (ideal hypothetical trial).

BY-COVID is funded by the European Union's Horizon Europe research the European Union and innovation programme under grant agreement number 101046203.

[figure not shown]

Figure 2. Timeline of the sequential emulated target trial (actual study design reusing Real World Data).

BY-COVID is funded by the European Union's Horizon Europe research the European Union and innovation programme under grant agreement number 101046203.

Sources of information

The analysis requires the secondary use of individual level data from COVID-19 registries (COVID-19 public health surveillance and monitoring information system of COVID-19 cases and SARS-CoV-2 vaccination population registry), insurance registry or health system users databases (*i.e., patient administrative information*) or data from Electronic Health Records (EHR, *i.e., comorbidities*), and death registration data. All data sources contain routinely collected data both from healthcare or public health information systems. For the variables required for the study, we refer to the common data model specification published in Zenodo (14).

A full join of the COVID-19 cases and SARS-CoV-2 vaccination records, linking all registries using unique pseudonyms at individual level, will be performed to obtain all people vaccinated with at least one dose of the SARS-CoV-2 vaccine (any of the available brands) in a resident area and/or with a documented positive diagnosis (irrespective of the type of test) for SARS-CoV-2 infection (COVID-19). In addition, linkage of patient administrative information and information on patient comorbidities is required to account for confounding factors (age, gender, comorbidities, immune status, foreign, pregnancy, residence area, essential worker, institutionalised) in the causal inference analysis. Data extraction is foreseen from the first date of a documented SARS-CoV-2 infection in the population until the most recent date at which data is available at the time of analysis. Park et al. (15) adopted a comparable approach to obtain data from the Korean COVID-19 vaccine effectiveness cohort, in their study comparing the effectiveness of two vaccines in preventing SARS-CoV-2 infection. They linked a registry with all COVID-19 laboratory-confirmed cases and a registry with SARS-CoV-2 vaccination data in South Korea.

Each country/region (Aragon (Spain), Belgium, Austria, Finland; Norway, Estonia and The Netherlands) will pull the data from their respective data sources conditional on data availability and access.

Participants

The analysis will be based on the secondary use of routinely collected data, individuals are not recruited. The study population consists of all residents of a country/region vaccinated with at least one dose of any SARS-CoV-2 vaccine and those eligible to be vaccinated with a documented positive diagnosis for SARS-CoV-2 infection (irrespective of the type of test) during the data extraction period. People who are not a resident of the participant country or region and people who have had a documented confirmed SARS-CoV-2 infection before completing the primary vaccination schedule (i.e. enrolment) or before January 1, 2021 (SARS-CoV-2 vaccine roll-out) for those not having completed a primary vaccination

BY-COVID is funded by the European Union's Horizon Europe research the European Union and innovation programme under grant agreement number 101046203.

schedule (i.e. matched controls), are excluded from the analysis. Sample sizes will depend on the data available in the data sources.

Statistical analysis plan

An initial exploratory and data quality analysis will be performed, checking pre-specified validation rules and missingness. Imputation will be performed in variables considered as core variables for the analysis.

Randomization is mimicked by matching on all confounding factors required to ensure comparability (conditional exchangeability) of the groups defined by vaccination (as identified in the Directed Acyclic Graph, see causal model specification published in Zenodo (13)). For each day during the enrollment period (i.e., sequential emulated trial), all newly vaccinated individuals (i.e. those having completed the primary vaccination schedule) will be matched in a 1:1 ratio to unvaccinated (or partially vaccinated) controls based on the variables listed in the adjustment set to close non-causal backdoor paths and so, eliminate confounding bias (16): age, gender, residence area, pregnancy, being an essential worker, being institutionalised, being a foreigner, presence of comorbidities, and the immune status. Presence of comorbidities is defined as having one of the following conditions: diabetes, obesity, health failure, COPD, a solid tumour without metastasis, chronic kidney disease, sickle cell disease, chronic liver disease, and hypertension (see the data model specification published in Zenodo (13) for variable-level specification, including data dictionaries and crosswalks defining each variable using several international disease *classification systems*). Immune status is defined as having one of the following conditions: HIV infection. blood cancer, transplantation, primary immunodeficiency, immunosuppression (see the data model specification published in Zenodo (13) for variable-level specification and crosswalks).

The matching will be performed using exact matching (whenever possible) or distance based algorithms such as nearest neighbour matching based on the Mahalanobis distance based on the probability of intervention (vaccination) for those individuals not matched using exact matching. Covariate balance after matching will be evaluated considering mean differences between variable values (standardised for continuous variables) between vaccinated and unvaccinated groups, with a difference of 0.1 or less considered to be acceptable.

For each person, follow-up ends at the occurrence of the outcome event (i.e., a confirmed SARS-CoV-2 infection), death (all causes), completing primary vaccination (for unvaccinated or partially vaccinated controls), completing primary vaccination of the matched control (for vaccinated persons), vaccination with a booster dose (for vaccinated persons), vaccination with a booster dose of the matched vaccinated person (for unvaccinated or partially vaccinated controls), or the end of the study period (i.e., the most

BY-COVID is funded by the European Union's Horizon Europe research the European Union and innovation programme under grant agreement number 101046203.

recent date at which data is available at time of analysis). Newly vaccinated persons (completing a primary vaccination schedule) are eligible for inclusion in the study, even if they have previously been selected as a control. As such, the matched controls enrolled at a particular day during the enrollment period are those who are unvaccinated (or partially vaccinated) at this date but may receive a first (or second) vaccination dose at a later date during the data extraction period.

Differences in the occurrence of a SARS-CoV-2 infection (as a time-to-event outcome) between primary vaccinated and unvaccinated or partially vaccinated individuals (average treatment effect, ATE (16)) will be computed by using adjusted Cox proportional-hazards models (17), and hazard ratios (HRs) and a robust variance estimate will be obtained.

A secondary analysis will be performed where the effectiveness of primary vaccination in preventing SARS-CoV-2 infection is assessed for different vaccine brands (e.g. BioNTech-Pfizer, Moderna, Johnson-Johnson, Astrazeneca, Novavax), hence conducting a stratified analysis using the matched pairs constructed for the primary analysis. Further, we can assess vaccine effectiveness during different time periods, with a dominant circulation of different SARS-CoV-2 variants.

Several sensitivity analyses will be performed accounting for different imputation algorithms, and different matching algorithms and compared in covariate balance after matching, robustness of the survival estimate and computing efficiency of the algorithm.

HRs and variance estimates will be collected from each country or region, and a meta-analysis will be performed in which the HRs are pooled by using the inverse variance method (18).

Ethical aspects

Balance risk/benefit

It is a population-wide retrospective observational longitudinal study, based on the secondary use of routinely collected social, health and care data from healthcare systems. As such, the intervention already took place preceding the study and there is no risk associated with participating in the study. Potential benefits derived from the study would be applied to the design and development of future vaccination programs at population level.

BY-COVID is funded by the European Union's Horizon Europe research the European Union and innovation programme under grant agreement number 101046203.

Treatment of personal data

Pseudonymized individual level data will be managed and analysed within the premises of contributing partners (data hubs, i.e. any institution holding or having access to the data), according to a predefined data model (14) specific to the research question (minimisation principle). Data is securely stored within the premises of the participant data hub. Access to this environment will only be provided to researchers involved in the completion of the project. All people authorised to manage the data will be subject to a non-disclosure agreement (NDA). Pseudonymized individual level data will only be processed for uses within the scope of the purposes of the present study and will not be shared with any third party. An analytical pipeline, developed by the project coordination hub, will be implemented within the secured processing environment using the transformed data as input. Extraction of aggregated results from the secured processing environment might be required to complete the purposes of the project involving comparative analysis between countries/regions. All country/region disclosure policies will be respected when producing and sharing aggregated outputs for comparison or publication. Finally, the scripts of the analytical pipeline and outputs will be published as open source using Zenodo using a CC-BY 4.0 International licence following the FAIR principles. In addition, the workflow can be also documented and published as an RO-Crate using WorkflowHub, in coordination with BY-COVID WP4. A Data Management Plan (DMP) is produced using ARGOS (OpenAIRE) and is subsequently published in Zenodo (19). The DMP will continuously be updated as new nodes join the baseline use case.

Healthcare implications

There are no implications for healthcare processes. Results of this study could potentially influence future decisions on public health interventions (i.e., future vaccination campaigns).

Informed consent

Informed consent is waived based on art. 6 and 9 of the GDPR. The collection is allowed based on general interest (art. 6 GDPR) and regarding article 9 § 2 of the GDPR: processing is necessary for reasons of public interest in the area of public health, such as protecting against serious cross-border threats to health, or ensuring high standards of quality and safety of health care and of medicinal products or medical devices, on the basis of Union or Member State law which provides for suitable and specific measures to safeguard the rights and freedoms of the data subject, in particular, professional secrecy.

BY-COVID is funded by the European Union's Horizon Europe research the European Union and innovation programme under grant agreement number 101046203.

Use of biological samples

No biological sample tissues, embryos or totipotential cells will be used. No genetic analyses will be performed.

Compensation to study participants

No compensation is provided to study participants.

Insurance policy

No insurance policy is required.

Conflict of interest

The researchers declare no conflict of interest.

Chronogram

Duration of this research project is until 30 September 2024.

Funding

BY-COVID Project funds. BY-COVID (BeYond COVID) is a Horizon Europe funded project, launched in October 2021 (20). Timeline: 1 October 2021 - 30 September 2024

References

- 1. Gobierna de Aragón. COVID-19. Situación actual | Transparencia Aragón [Internet]. 2023 [cited 2023 Jan 10]. Available from: https://transparencia.aragon.es/COVID19
- 2. Sciensano. Belgium COVID-19 Dashboard Sciensano [Internet]. 2023 [cited 2023 Jan 10]. Available from: http://lookerstudio.google.com/reporting/c14a5cfc-cab7-4812-848c-0369173148ab/p
- age/p_j1f02pfnpc?feature=opengraph 3. Hernán MA, Robins JM. Using Big Data to Emulate a Target Trial When a Randomized Trial Is Not Available. Am J Epidemiol. 2016 Apr 15;183(8):758-64.
- 5. Chuenkitmongkol S, Solante R, Burhan E, Chariyalertsak S, Chiu NC, Do-Van D, et al.

Funded by the European Union

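### Controls are screened for prior infection at 1 January 2021 instead of at their matched time zero, so already-infected controls qualify

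*Protocol*

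**What the plan says.** In the Eligibility criteria row of Table 1, the target trial applies a single criterion to everyone: "Individuals without a SARS-CoV-2 infection before enrolment".

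The emulation column of the same row uses two dates. It admits "Individuals without a documented confirmed infection before completing the primary vaccination schedule (i.e. enrolment) or before January 1, 2021 (SARS-CoV-2 vaccine roll-out", and it attaches the January date to one group: "for those not having completed a primary vaccination schedule (controls". The Participants section turns the same rule into an exclusion. It removes "people who have had a documented confirmed SARS-CoV-2 infection before completing the primary vaccination schedule (i.e. enrolment) or before January 1, 2021", again tying the January date to people without a completed schedule, whom it identifies as the matched controls.

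The Follow-up period row of Table 1 starts a control's clock at the "first eligible time (time of completing a primary vaccination schedule of the matched pair". The Statistical analysis plan section adds that matched controls "may receive a first (or second) vaccination dose at a later date during the data extraction period" and that re-entry is allowed: "Newly vaccinated persons (completing a primary vaccination schedule) are eligible for inclusion in the study, even if they have previously been selected as a control".

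**The concern.** In a sequence of nested daily trials, both members of a pair have to meet the eligibility criteria on the day the pair is formed. The vaccinated member does: own completion is both the date of the infection check and time zero. The control is checked at a fixed calendar date that can lie months before time zero.

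People with a documented infection between those two dates can therefore enter the control group but not the vaccinated group. If infection protects against a further documented infection, the comparison group carries immunity that its partners cannot have. The control event rate falls, the hazard ratio rises, and vaccine effectiveness is understated. The same pipeline is to run in every country or region and the hazard ratios are to be pooled by inverse variance. A shared bias would survive pooling, and sites that resolve the wording differently would add artificial heterogeneity.

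**Working it through.** The protocol gives no sample size, event count or power figure, so there is nothing to reproduce. The check is a reading of the rule against time zero, followed by an illustration of size.

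**1. The gap.** Enrolment runs from 1 January to 1 September 2021: 31 + 28 + 31 + 30 + 31 + 30 + 31 + 31 = 243 days. This is the largest possible distance between the control's infection check and the matched time zero.

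**2. Whether anything else closes it.** The adjustment set (Table 1, Assignment procedures; Statistical analysis plan) is age, gender, residence area, pregnancy, essential worker, institutionalised, foreign, comorbidities and immune status. Prior infection is not in it. No other sentence requires a control to be infection-free at time zero.

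**3. Example.** Two people are paired in July 2021. A documented infection in March 2021 bars the vaccinated member but not the control.

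**4. Record handling.** Follow-up ends at diagnosis. For the March control, the end date precedes the July start date. The protocol does not say whether such a record is dropped, kept at risk, or counted only on reinfection.

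**5. Approximate size if these controls are kept as immune.** If a share p of controls is immune but stays in the risk set, the control rate is multiplied by about (1 − p), and the hazard ratio by about 1/(1 − p).

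A simulation of daily 1:1 matching supplied p and checked this. From the protocol: the enrolment dates, the 168-day limit and 1 March 2022 end of the target trial, and 17% never completing (100% − 83%, the Belgian coverage in the introduction). Assumed: 300,000 people, a constant infection hazard, completion spread evenly over days 30 to 300 and independent of infection, no reinfection, no confounding, and the rate ratio standing in for the hazard ratio.

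| Daily hazard | p | 1/(1 − p) | Simulated, true HR 1.0 | Simulated, true HR 0.3 |
|---|---|---|---|---|
| 0.0002 | 2.7% | 1.03 | 1.00 | 0.29 |
| 0.0005 | 6.4% | 1.07 | 1.08 | 0.33 |
| 0.001 | 12.3% | 1.14 | 1.14 | 0.34 |

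At the lowest hazard there were 3,983 vaccinated and 3,999 control events, so the standard error of the log ratio is about √(1/3983 + 1/3999) = 0.022. The simulated 1.00 is therefore compatible with the expected 1.03.

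**6. The same simulation with a time-zero check on both members.** It returns 0.99 to 1.01 for a true ratio of 1.0, and 0.295 to 0.302 for 0.3.

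**7. The person-level reading.** Suppose anyone infected before their own completion is removed from the study altogether. A control who completes later is censored at completion, so any event that person has as a control comes before completion and triggers removal. If f is the share of control events arising in later completers, the ratio is multiplied by about 1/(1 − f). At a hazard of 0.0005, simulated control events fell from 9,493 to 4,138, so f = 1 − 4138/9493 = 56%, and 1/(1 − 0.56) = 2.3. Across the three hazards a true ratio of 1.0 came out at about 2.3 to 2.5. With f = 42% the factor would be 1/(1 − 0.42) = 1.7. The protocol does not supply f.

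**The case against.** The strongest reply has four parts.

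- **The vaccinated clause is correct.** A reader might infer that the infection check is mistimed in both groups. It is not: own completion is the vaccinated member's time zero. This stands, and the fault lies on the control side alone.
- **Deletion of control events is the weaker reading.** A reader might infer from Participants that later completers infected while serving as controls are removed, and that the hazard ratio roughly doubles. The wording there permits this but does not establish it. Both statements of the rule tie the January date to the control role, and the section on target trial emulation treats a person as a new individual at each eligible time. On that footing a later completer is judged as a control for that person-trial, and no event is lost. This largely stands, and the larger figures should not be presented as the expected bias.
- **The admitted controls may do little harm.** If records with an end date before the start date are dropped, they contribute no person-time and most of the bias goes. That is a fair point about size, but the text does not say it, and the vaccinated partner would then have no control.
- **Eligibility may be implied at each time.** Data extraction starts early in order to identify previous infections, and daily matching is among eligible individuals. However, the only infection criterion written for controls is the January one, so eligibility leads back to it.

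It is also true that the simulation used a full population, whereas Table 1 admits only people with a vaccine dose or a positive diagnosis. The figures illustrate direction and order of size only.

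**Conclusion.** The criterion is wrong as written for controls. It departs from the protocol's own target trial, and matching cannot repair it. This is a stated rule in two places, so it is not a detail left for a separate analysis plan.

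On the reading that best fits the text, the bias is modest: about 1.00 to 1.14 for a true hazard ratio of 1.0, and 0.29 to 0.34 for a true 0.3. That rests on the assumed hazards and on already-infected controls being kept at risk as immune. It is negligible at the lowest hazard. Under the person-level reading the upward bias would be substantial, but neither that reading nor its size can be settled from the protocol. The defect itself depends on none of these assumptions.

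**What to change.** Replace the prior-infection rule in the emulation column of Table 1 and in Participants with one criterion for both members of a pair, reassessed in each daily trial: no documented infection from the start of data extraction up to that trial's time zero.

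Add that an infection after time zero counts only as an outcome for that person-trial and never removes it. Someone infected while serving as a control keeps that event and cannot later join the vaccinated group, which the existing clause for completers already implies.

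The cost is one sentence in each of the two places and one eligibility filter in the shared pipeline. The infection dates are already extracted from the first documented infection onward, so no new data are needed.
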